15.12 Modified Hoehn and Yahr

Modified Hoehn and Yahr PD Staging

The Modified Hoehn and Yahr PD Staging is a scale expressing the severity of the symptoms of PD. It provides a practical classification of 5 stages of ever increasing severity. The stages are defined as:

Stage 0	=	No signs of disease.
Stage 1	=	Unilateral disease.
Stage 1.5	=	Unilateral plus axial involvement.
Stage 2	=	Bilateral disease, without impairment of balance.
Stage 2.5	=	Mild bilateral disease, with recovery on pull test.
Stage 3	=	Mild to moderate bilateral disease; some postural instability; physically independent.
Stage 4	=	Severe disability; still able to walk or stand unassisted
Stage 5	=	Wheelchair bound or bedridden unless aided.

Hoehn MM, Yahr MD (1967). Parkinsonism: onset, progression and mortality. *Neurology*. 17(5):427-42.

15.13 Fall Questionnaire

Fall Questionnaire

Baseline (Visit 2):

Have you been experiencing falls over the past 3 months? Yes/No

If yes, approximately how many falls have occurred in the past 3 months?

At Week 24 (Visit 7), Week 48 (Visit 11) and Week 76 (Visit 13):

Have you been experiencing falls over the past 3 months? Yes/No

If yes, approximately how many falls have occurred in the past 3 months?_____

In the event of an Early Termination Visit (Part A or B):

Have you been experiencing falls over the past 3 months? Yes/No If yes, approximately how many falls have occurred in the past 3 months?

15.14 Healthcare Resource Utilization Questionnaire

Healthcare Resource Utilization Questionnaire

INPATIENT ADMISSIONS

Instructions: Please record in the table below all inpatient admissions since the subject's last scheduled clinic visit. Do not include inpatient admissions for the facilitation of assessments specific to this protocol not associated with any deterioration in condition.

- If the subject had no inpatient admissions since the last scheduled clinic visit, please check the appropriate box below.
- If the patient was hospitalized since the last scheduled clinic visit, please record the admission and discharge dates of each hospitalization. Also indicate if the type of each admission was Parkinson's disease (PD)-related or Non-PD related along with the reason for each admission, e.g. pneumonia, which should be consistent with source documentation and eCRF entries.

	source documentation and eCRF entries.							
	☐ No inpatient admissions since the subject's last scheduled clinic visit							
Admission Date (dd / mmm / yyyy) Discharge Date (dd / mmm / yyyy) Type of Admission Reason for Admission								
1.	'	//	☐ PD-relate					
2.	'	//	☐ PD-relate					
3.				ated D related				
		EMERGENC	V DOOM (FI	D) VICITO				
	 Instructions: Please indicate how many times the subject visited an Emergency Room since the last scheduled clinic visit for PD-related and non-PD related reasons. If the subject had no emergency room visits since the last scheduled clinic visit, please check the appropriate box below. If the subject visited the emergency room since the last scheduled clinic visit, please record the date of each visit. Also indicate if the visit was PD-related or Non-PD related along with the reason for each visit, e.g. pneumonia, which should be consistent with source documentation and eCRF entries. 							
[☐ No emergency room visits since the subject's last scheduled clinic visit							
	ER Visit Date (dd / mmm / yyyy)	Type of E	R Visit	I	Reason for ER Visit			
1.	//	□ PD-related □ Non-PD rela	nted					
2.	/ /	□ PD-related						

3.

☐ Non-PD related

□ Non-PD related

☐ PD-related

1 INTRODUCTION

TOZ-CL05 will include a 24-week double-blind phase (Part A) followed by a 52-week open-label phase (Part B). This statistical analysis plan (SAP) describes the statistical methods to be used during the reporting and analyses of data collected under Part A (double-blind phase) of Biotie's Protocol TOZ-CL05. The SAP for Part B (open-label phase) will be submitted at a later date. The SAP was developed to support Biotie's Special Protocol Assessment (SPA).

This SAP should be read in conjunction with the study protocol and the SPA document. This version of the plan has been developed using final protocol Amendment No. 1, dated 19 May 2015.

Table, figure and listing (TFL) shells will be developed at a later date.

2 STUDY OBJECTIVES

2.1 Primary Efficacy Objective for Part A (double-blind phase)

 To demonstrate the efficacy of the A2a receptor antagonist tozadenant in the treatment of levodopa-treated PD patients experiencing end-of-dose "wearing-off", based on the change from Baseline to Week 24 in the number of hours per day spent in the OFF state.

2.2 Key Secondary Efficacy Objectives for Part A (double-blind phase)

- 1) To evaluate the effect of tozadenant on good ON time (defined as the sum of ON time without dyskinesia and ON time with non-troublesome dyskinesia).
- 2) To evaluate the effect of tozadenant on Unified Parkinson's Disease Rating Scale (UPDRS) Parts II (Activities of Daily Living [ADL] subscale) + III (motor subscale) total scores.

2.3 Other Secondary Efficacy Objectives for Part A (double-blind phase)

- 1) To evaluate the effect of tozadenant on investigator global impressions of improvement (Clinical Global Impression of Improvement [CGI-I]).
- 2) To evaluate the effect of tozadenant on patient global impressions of improvement (Patient Global Impression of Improvement [PGI-I]).
- 3) To evaluate the effect of tozadenant on UPDRS Part III (motor subscale) scores in the ON state.
- 4) To evaluate the effect of tozadenant on investigator global impressions of severity of illness (Clinical Global Impression of Severity [CGI-S]).
- 5) To evaluate the effect of tozadenant on UPDRS Part II (ADL subscale) scores.
- 6) To evaluate the effect of tozadenant on the number of hours per day spent in the ON state without dyskinesia, with non-troublesome dyskinesia, or with troublesome dyskinesia.
- 7) To evaluate the effect of tozadenant on the number of hours per day spent in the ON state without dyskinesia.

8) To evaluate the effect of tozadenant on the number of hours per day spent in the ON state with any dyskinesia (troublesome or non-troublesome).

CONFIDENTIAL

- 9) To evaluate the effect of tozadenant on the number of hours per day spent in the ON state with non-troublesome dyskinesia.
- 10) To evaluate the effect of tozadenant on PD-related quality of life as measured by Parkinson's Disease Quality of Life Questionnaire (PDQ-39) (total score and individual domain scores).
- 11) To evaluate the effect of tozadenant on UPDRS Part IV.
- 12) To evaluate the effect of tozadenant on UPDRS Part I.

2.4 Safety Objectives (Part A)

- 1) To evaluate the safety and tolerability of tozadenant in levodopa-treated PD patients experiencing end-of-dose "wearing-off", based on assessment of adverse events (AEs), vital signs, electrocardiograms (ECGs), physical and neurological exams, and clinical laboratory tests.
- 2) To evaluate the effects of tozadenant on the occurrence of daytime drowsiness (including episodes of sudden onset of sleep), impulsive behavior, and suicidality.

3 STUDY DESIGN

This is a Phase 3, international, multicenter, randomized, double-blind, placebo-controlled, parallel-group, 3-arm study with an open-label phase in levodopa-treated patients with PD experiencing end-of-dose "wearing-off". This study includes a Screening Period of up to 6 weeks that starts with a Screening Visit, a 24-week Double-Blind Treatment Period, a 52-week Open-Label Treatment Period, and a Safety Follow-Up Visit 4-weeks post-treatment. After providing written informed consent, patients will undergo screening evaluations. Patients must meet all inclusion criteria and none of the exclusion criteria, and they must successfully complete the diary training and achieve 80% overall diary concordance with the PD diary trainer/rater including at least 1 OFF interval to be considered for randomization. If preliminary eligibility is confirmed by the investigator and the Sponsor/Sponsor's designee, patients will then be scheduled for a Baseline Visit and will be required to return a valid set of Baseline diaries. Final eligibility will be determined at the Baseline Visit.

Eligible patients will be randomized in Part A to receive 1 of 2 tozadenant doses (60 mg BID or 120 mg BID) or placebo in a ratio of 1:1:1. Blinded IMP will be dispensed to patients at each study visit and will be taken BID (approximately 12 hours apart) for 24 consecutive weeks. Patients will return to the study site for evaluation at Weeks 2, 6, 12, 18, and 24. Patients will be contacted by telephone before the start of each 3-day PD diary completion period to be reminded to complete the diary for 3 consecutive days prior to their next scheduled visit. Unscheduled visits can be arranged as considered necessary by the investigator. In the event of Early Termination during Part A, patients will be asked to complete an Early Termination Visit as soon as possible and then return 28 ± 3 days after their last dose of IMP for a Post-Early Termination Safety Follow-Up Visit. Blinded safety data from the double-blind phase (Part A) will be provided to the Data and Safety Monitoring Board (DSMB), at a frequency specified by the DSMB charter, for ongoing monitoring of safety and detection of any trends. If requested by the DSMB, the DSMB statistician will provide unblinded safety data to the DSMB on a per needed basis, to enable a fully informed review.

The Schedule of Events/Evaluations for Part A is shown in **Table 3-1**.

Table 3-1: Part A – Schedule of Events/Evaluations

TOZ-CL05 PART A: DOUBLE-BLIND PHASE

Study Period	Screening a	Baseline Predose	Double-Blind Treatment (24 weeks)				Early Termination ^x	Fo	
Study Week	-6 to -1	BL	2 (±3 d)	6 (±3 d)	12 (±3 d)	18 (±3 d)	24 (±7 d)		28
Assessments Study Visit		V2	V3	V4	V5	V6	V7	A98	
Written informed consent	X								
Patient to view study-provided video ("What to expect during this clinical trial")	X				X				
Demographic data, medical history, including neurological and PD history	X								
Recording of concomitant and anti-PD medications	X	X	X	X	X	X	X	X	
BP b, pulse b	X c	X c	X	X	X	X	X	X	
Weight (include height at Screening)	X						X	X	
Physical and neurological examination	X						X	X	
Caffeine Intake Questionnaire		X							
PD diary training and diary concordance session	X								
12-lead ECG ^e	X	X	X	X	X	X	X	X	
Modified Hoehn and Yahr staging (observed ON; OFF estimated per history)	X								
UPDRS Parts I, II, III, and IV (in ON state) ^f	X	X	X	X	X	X	X	X *	
MMSE-II (in ON state)	X								
mMIDI ^g	X			X	X	X	X	X	
C-SSRS	X	X	X	X	X	X	X	X	
Sponsor eligibility review	X								
PD diary collection (phone call prior to start of 3 consecutive 24-hour diary completion periods)	X h	X ^h	Xi	X i	X i	X i	X i	X j, x	

Table 3-1: Part A – Schedule of Events/Evaluations (continued)

TOZ-CL05 PART A: DOUBLE-BLIND PHASE

Study Period	Screening a	Baseline Predose						Fo	
Study Week	-6 to -1	BL	2 (±3 d)	6 (±3 d)	12 (±3 d)	18 (±3 d)	24 (±7 d)		28
Assessments Study Visit	V1	V2	V3	V4	V5	V6	V7	A98	
PD diary review	X	X	X	X	X	X	X	X ^j	
Final verification of inclusion and exclusion criteria		X							
Patient randomization		X							
CGI-I k			X	X	X	X	X	X x	
PGI-I k			X	X	X	X	X	X x	
CGI-S k		X	X	X	X	X	X	X x	
SCOPA-cog k		X					X	X	
PDQ-39 k		X			X	X	X	X	
EQ-5D-5L k		X					X	X	
TSQM-9 k				X			X	X	
Sudden onset of sleep		X	X	X	X	X	X	X	
ESS		X	X	X	X	X	X	X	
Fall questionnaire		X					X	X	
Healthcare Resource Utilization			X	X	X	X	X	X	
IMP dispensing and return ¹		X	X	X	X	X	X	X	
Recording of AEs	X m	X m	X	X	X	X	X	X	
Anti-PD medications			Patient	s continue	stable dose	of levodop	a and other a	llowed anti-PD medic	cation
FSH test, females who are postmenopausal for < 2 years	X								
Thyroperoxidase antibody	X								
Laboratory tests: hematology ⁿ , chemistry ^o (including thyroid ^p)	X	X	X	X	X	X	X	X	
Urine pregnancy test, females of childbearing potential q	X	X	X	X	X	X	X	X	
Urinalysis ^r	X	X	X	X	X	X	X	X	
Tozadenant blood sampling s		X	X ^t	X	X	X	X ^t	X ^t	
Pramipexole blood sampling (applicable patients only)		X u	X v	X	X	X	X v	Χ ^ν	
eCRF completion	X	X	X	X	X	X	X	X	

Table 3-1: Part A – Schedule of Events/Evaluations (continued)

TOZ-CL05 PART A: DOUBLE-BLIND PHASE

AE, adverse event; BP, blood pressure; CGI-I, Clinical Global Impression of Improvement; CGI-S, Clinician Global Impression of Sever Severity Rating Scale; d, day(s); ECG, electrocardiogram; eCRF, electronic case report form; EQ-5D-5L, EuroQol 5D-5L Health Questic Sleepiness Scale; ET, Early Termination; FSH, follicle stimulating hormone; IMP, investigational medicinal product; mMIDI, Modified Interview; MMSE-II, Mini-Mental State Exam—Second Edition (MMSE-II); P, pulse (beats per minute); PD, Parkinson's disease; PDQ-3 of Life Questionnaire; PGI-I, Patient Global Impression of Improvement; SCOPA-cog, Scales for Outcomes in Parkinson's Disease - cog Satisfaction Questionnaire for Medication; UPDRS, Unified Parkinson's Disease Rating Scale; V, Visit.

Part A - Footnotes:

- ^a Screening Period may not exceed 6 weeks.
- b Obtain and record BP and pulse measurements after at least 5 minutes supine rest and again after standing for approximately 1 minutes
- ^c At Screening and at Baseline (before dosing), obtain and record serial BP and pulse measurements after at least 5 minutes supine rest a approximately 1 and 3 minutes, on 3 occasions approximately 10 minutes apart.
- d Optional assessments that may be performed for evaluation of AEs, at the investigator's discretion.
- ^e Resting supine 12-lead ECGs will be collected after the patient has been in a supine position for a minimum of 5 minutes. ECGs should visit when the patient is not experiencing dyskinesia that would interfere with an adequate recording. At Baseline, obtain triplicate 12-le performed several minutes apart).
- f UPDRS to be measured in ON state approximately 1 to 3 hours after patients have taken a scheduled dose of levodopa (preferably their Patients will be instructed to have already taken their normally scheduled dose of levodopa (and their IMP for visits following randomi study site in order to have their UPDRS Part III evaluated in the ON state. UPDRS in the ON state will be measured at a time represent patient, not in the patient's "best" ON.
- At Screening, send patient for structured clinical interview if one or more positive mMIDI modules. If the structured clinical interview not have an ICD, he/she will not be considered ineligible on that basis. After Baseline, if patient has one or more positive modules on the participation in the study should be discussed with the Medical Monitor.
- h The 3-day practice diary during the Screening Period and the 3-day Baseline diary must both be valid in order to randomize a patient. The patient before the scheduled start of the diary completion periods to remind him or her to keep the PD diary and to review completion in be reminded to send the completed practice diary to the trainer/rater and to bring their Baseline diary to the Baseline Visit. If the practice the patient may be retrained and complete another practice or Baseline diary within the 6-week window of the Screening Period, if the patient study.
- PD diary collected over the 3 consecutive 24-hour periods before the day of the scheduled study visits on Week 2, 6, 12, 18 and 24. The the patient before the scheduled start of the 3-day PD diary completion period (at the latest, on the last working day before the schedule completion) and review completion instructions. The patient will also be reminded to bring their PD diary to the visit. The trainer/rater diary contains missing and/or invalid entries to reinforce instructions for appropriate completion.
- Done only if the ET date coincides with the scheduled diary collection return date.
- ^k To be collected during patient's ON state.
- Patients will be instructed to take two (2) tablets of the dispensed blinded IMP by mouth twice daily (BID), in the morning and in the e time each day, for a total of four (4) tablets per day. The evening dose should be approximately 12 hours after the morning dose. Patien morning and evening doses at least 1 hour before or 2 hours after a meal and to refrain from eating for at least 1 hour after dosing.
- ^m Pretreatment AEs.

Table 3-1: Part A – Schedule of Events/Evaluations (continued)

TOZ-CL05 PART A: DOUBLE-BLIND PHASE

- ⁿ Hematology tests: Hemoglobin concentration, hematocrit, red blood cell count, total and differential white blood cell, thrombocyte (pla
- ^o Blood chemistry (including liver function) tests: Aspartate amino transferase (AST), alanine amino transferase, (ALT), gamma-glutamy phosphatase (ALP), lactate dehydrogenase (LDH), total bilirubin (conjugated and unconjugated), albumin, creatinine, urea/blood urea uric acid, total protein, sodium, chloride, potassium, calcium, phosphate, glucose, cholesterol, creatine phosphokinase (CK). Regarding Screening, refer to Exclusion Criterion #25 (Section 4.2).
- ^p TSH, free T3, and free T4.
- ^q Document method of contraception at Screening and verify continuation of (or any change to) contraceptive method at each visit. For f perform a urine pregnancy test.
- ^r Urinalysis: Specific gravity, pH, ketones, blood, protein, glucose. If urine dipstick is positive for leukocytes, protein, or erythrocytes, a culture will be performed.
- Solution PK blood samples will be collected for determination of tozadenant concentration levels at Baseline before dosing, at Weeks 2, 6, 12, 1 in the event of an Early Termination Visit unless the patient's last dose of IMP was taken more than 7 days before the visit. For Weeks 6 Termination, one (1) PK blood sample will be taken at the most convenient time at each visit. For Unscheduled Visits, one (1) PK blood investigator's discretion (e.g., for AEs thought to be study drug related). For each collection, the time of sampling and patient-reported the most recent IMP dosing prior to sampling will be recorded. See Section 8.1.
- Collection of two (2) tozadenant PK blood samples at Weeks 2 and 24 is required. The first sample will be taken on arrival and the second with the time between the blood samples being at least 45 minutes or longer and no IMP dosing between the two blood draws. (For an I blood samples are not required if the patient's last dose of IMP was taken more than 7 days before the Early Termination Visit.) See Second Seco
- Only for patients concomitantly taking pramipexole: PK blood sample collected for tozadenant will also be analyzed for plasma pramiperole predose). A second PK blood sample for plasma pramipexole concentration will be taken at Baseline at least 45 minutes after the first I
- Vonly for patients concomitantly taking pramipexole: PK blood samples collected for tozadenant will also be analyzed for plasma pramipote both samples collected at Weeks 2 (Visit 3) and 24 (Visit 7) and Early Termination Visit during Part A. If a tozadenant sample is not be Termination visit (patient's last dose of IMP was taken more than 7 days before the visit) a PK sample for plasma pramipexole concentration.
- Only for patients with potential pramipexole-related AEs: During Part A, in the event of AEs thought to be pramipexole-related (e.g., d delusions, hypotension, somnolence, nausea, vomiting), either noted at the time of a scheduled study visit or an Unscheduled Visit, PK tozadenant will also be analyzed for plasma pramipexole, i.e., at Week 6 (Visit 4), Week 12 (Visit 5) or Week 18 (Visit 6). If a tozaden at an Unscheduled visit a PK sample for plasma pramipexole concentration will be collected. See Section 8.2.
- ^x If patient has discontinued IMP, perform the Early Termination Visit as soon as possible after the last dose of IMP. Efficacy-related mea CGI-I, PGI-I, and CGI-S) will not be completed at an Early Termination Visit if patient stopped taking study drug more than 24 hours pressures during the Early Termination Visit. If patient took the last dose of IMP 28 or more days prior to the Early Termination Visit, a Follow-Up Visit (Section 6.2.24) is not required.

3.1 Analysis sets

If a subject receives at first dose a dose other than the dose randomized to, the table, figures and listings (TFLs) based on the safety analysis set will display a footnote describing the dosing error.

3.1.1 Intent-to-Treat Set (ITT)

The ITT according to the intention-to-treat principle will consist of all randomized patients. Patients will be accounted for in the treatment group to which they were originally randomized. Summaries of demographic and baseline data will be done in the ITT.

3.1.2 Safety Set (SS)

The SS will consist of all randomized patients who received at least one dose of IMP. Patients will be accounted for in the treatment group based on IMP actually received at first dose. Summaries and/or analyses of safety data will be done in the SS.

3.1.3 Modified Intent-to-Treat Set (mITT)

The mITT will consist of all randomized patients who took at least 1 dose of study drug and had valid diaries at baseline and had valid diaries on at least 1 post-baseline visit. Patients will be accounted for in the treatment group to which they were originally randomized.

Summaries and/or analyses of all efficacy data will be done in the mITT.

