3.1.4 Per Protocol Set (PPS)

The PPS will consist of all randomized patients who have an efficacy evaluation (number of hours per day spent in the OFF state while awake) at Week 24 and have no major protocol deviations/violations. In addition, subjects randomized to tozadenant must have measureable plasma concentrations at each post-baseline visit for the subject to be considered in the PPS (i.e. not have any below-the-limit-of-quantification result from the bioanalysis at any post-baseline visit). This will not exclude subjects who had missing samples or values, for any reason, from the analysis. (For example, instances where the analytical lab was unable to obtain a result from a sample they received, or no sample was received, or the bioanalytical results were considered invalid.)

Patients will be accounted for in the treatment group to which they were originally randomized.

Summaries and/or analyses of the primary endpoint and four key secondary endpoints will be done in the PPS.

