9.6.2 Imputation Rules using Multiple Imputation for Sensitivity Analysis

This section describes two methods for multiple imputation of missing data. With each imputation method, the analysis described in **Section 9.6.1** will be repeated using the mITT and PPS.

In addition, for each imputation method, a univariate ANCOVA will be performed at Week 24 which includes the model terms: country/region, treatment group and baseline value.

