9.6.2.2 Multiple Imputation Method

The sensitivity analysis described in this section is based on a particular assumption of missing not at random (MNAR), or non-ignorable missingness mechanism. For subjects who withdraw from one of the tozadenant treatment groups, the primary endpoint for missing weeks will be derived using multiple imputation based on the mean in the placebo group. Withdrawals from the placebo group will also be imputed based on the placebo data. Intermittent missing data, that is, data that is missing at one week but present at a later week, will be assumed to be missing at random (MAR) and will be imputed using a method appropriate for that assumption. When the missing data has been imputed, the primary endpoint data will be analyzed as a sensitivity analysis using the same method as the primary analysis.

There are two types of missing data that will be imputed:

- 1. Data that is missing at a specific week but present at a later week (intermittent missing data)
- 2. Data that is missing after a subject drops out (monotonic missing data)

The following process will be used to impute all types of missing values for the primary analysis: Step 1:

 For intermittent missing data, Markov Chain Monte Carlo (MCMC) simulation will be used to impute values.

The MCMC imputation process will follow the general pre-planned guidelines described below. However the ability of the process to converge can be dependent on the amount of data that is missing. Convergence of the process will be assessed after unblinding.

The number of burn in iterations will be set at 200, or higher if deemed necessary. The thinning option will be set to select one out of every 100 iterations to insure sufficient separation from previous iterations. Ten imputations will be the initial setting. Trace plots will be checked for

convergence. Factors included in the MCMC algorithm used to impute the missing values will be randomized treatment and the baseline value of the outcome variable.

CONFIDENTIAL

Step 2:

- 3. For monotone missing data, a regression model will be used to impute values as follows:
- 4. Subjects that do not have a Week 2 value or are in the Placebo arm are selected.
- 5. SAS PROC MI will be used to impute missing values using the Baseline time point.
- 6. The imputed data will be combined with the non-missing tozadenant data to achieve a database with data present for all subjects in the analysis set.

Step 3:

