9.6.3 Key Secondary Variables

All secondary variables will be analyzed by the same model as described for the primary outcome variable, with the baseline covariate value being the baseline outcome variable of interest included in the statistical model instead of the baseline number of hours of OFF time in the mITT and PPS. The sensitivity analyses described in **Section 9.6.2** will also be performed for the key secondary outcomes.

The following key secondary efficacy endpoints will be summarized and analyzed:

- Change from baseline to Week 24 in the number of hours per day spent in good ON time, defined as the sum of ON time without dyskinesia and ON time with non-troublesome dyskinesia.
- Change from baseline to Week 24 in UPDRS Parts II (ADL subscale) + III (motor subscale) total scores.

For the UPDRS Part I, II, III, sum of Parts II+III and I – III and Part IV (Part A, B and C and total) if a question making up the total score is missing, the total score for that Part will not be determined for the subject for the given visit, as well as the sum of Parts I - III. Subjects with missing total score will be footnoted.

CONFIDENTIAL

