9.6.4 Other Secondary Variables

All other secondary variables will be analyzed by the same model as described for the primary outcome variable, with the covariate value being the baseline outcome variable of interest included in the statistical model instead of the baseline number of hours of OFF time. The analyses will only be done in the mITT. No sensitivity analyses are planned and there will be no adjustment for multiplicity.

The following other secondary efficacy variables to be summarized and analyzed include: the change from Baseline to Week 24 (where applicable) for the following:

- 1. CGI-I at Week 24
- 2. PGI-I at Week 24.
- 3. UPDRS Part III (motor subscale) score in the ON state.
- 4. CGI-S.
- 5. UPDRS Part II (ADL subscale) score.
- 6. Number of hours per day spent in the ON state (without dyskinesia, with non-troublesome dyskinesia, or with troublesome dyskinesia).
- 7. Number of hours per day spent in the ON state without dyskinesia.
- 8. Number of hours per day spent in the ON state with any dyskinesia (troublesome or non-troublesome).
- 9. Number of hours per day spent in the ON state with non-troublesome dyskinesia.
- 10. PD-related quality of life as measured by PDQ-39 (total score and individual domain scores).
- 11. UPDRS Part IV score.
- 12. UPDRS Part I score.

For the UPDRS Part I, II, III, sum of Parts I – III and Part IV (Part A, B and C and total) if a question making up the total score is missing, the total score for that Part will not be determined for the subject for the given visit, as well as the sum of Parts I - III. Subjects with missing total score will be footnoted.

For the PDQ-39 questionnaire, if a question is not answered, then the total score or the dimension score for the PDQ-39 will not be determined for the subject at the visit. Missing data will be footnoted.

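### Patients with no valid post-baseline diary are left out of both the placebo-based imputation and the UPDRS II+III test; the effect is probably small and SAP wording can fix it

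*SAP*

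**What the plan says.** **Analysis sets.** SAP 3.1.3 defines the mITT as randomized, dosed patients who "had valid diaries at baseline and had valid diaries on at least 1 post-baseline visit"; protocol 11.1 has the same definition. Its scope is complete: "Summaries and/or analyses of all efficacy data will be done in the mITT". The ITT has another use (SAP 3.1.1): "Summaries of demographic and baseline data will be done in the ITT". The only other efficacy set, the PPS (SAP 3.1.4), is narrower on dropout. It admits patients "who have an efficacy evaluation (number of hours per day spent in the OFF state while awake) at Week 24" with no major deviation.

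**Imputation.** Under SAP 9.6.2 the primary analysis, with each imputation method, "will be repeated using the mITT and PPS". SAP 9.6.2.2 imputes tozadenant withdrawals from placebo data. Its first monotone step, which uses baseline alone, reads: "Subjects that do not have a Week 2 value or are in the Placebo arm are selected". Protocol 11.4.1 gives the purpose of the sensitivity analyses as judging the effect of missing observations.

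**UPDRS.** SAP 9.6.3 models the key secondaries, UPDRS II+III among them, with the endpoint's own baseline in place of "the baseline number of hours of OFF time in the mITT and PPS". For the other secondaries, which include the remaining UPDRS scores, SAP 9.6.4 says: "The analyses will only be done in the mITT". SAP 5.5 gives UPDRS its own validity rule (Part III completed in the ON state), which does not mention diaries.

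**Collection.** The first post-baseline diary and the first post-baseline UPDRS both fall at Week 2 (SAP Table 3-1). At Early Termination a diary is taken only if the date coincides with a scheduled diary return. UPDRS has no such condition, but is not done if study drug stopped more than 24 hours earlier (protocol 6.2.32).

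**The concern.** Membership of the mITT depends on data seen after randomization. Two consequences follow.

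First, the placebo-based imputation is the plan's stress test for withdrawal, yet it cannot reach patients who withdraw before producing a valid diary. The algorithm has a step that could impute them from baseline, but the analysis set has already removed them.

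Second, UPDRS II+III is test 3 in SAP 9.6.6.1, and all three 60 mg tests wait behind it. Letting one instrument's completeness decide who enters the test of another discards valid data on a confirmatory endpoint and adds a selection step with no bearing on that endpoint.

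**Working it through.** **1. Who is left out of the OFF-time imputation**

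- SAP 9.6.2.2 Step 1 fills intermittent gaps, meaning a missing week followed by an observed one.
- After Step 1, a patient still without a Week 2 value has no later value either, so has no post-baseline OFF time at all.
- Such a patient has no valid post-baseline diary and is not in the mITT. The PPS also excludes them, since it needs a Week 24 value.
- For OFF time, the first monotone step therefore has no tozadenant patient to impute.
- A patient who withdraws after one valid diary visit stays in the mITT and is imputed from placebo. So can a patient whose early termination coincides with the Week 2 diary return.

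**2. The plan's own power figure**

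Inputs (SAP 3.2): n = 150 per arm, difference 0.9 h, SD 2.6 h, two-sided alpha 0.05.

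- SE = 2.6 × √(2/150) = 0.300 h, and 0.9 / 0.300 = 3.00.
- Power is 85.0% by the normal approximation and 84.8% by noncentral t. The stated 85% reproduces.

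**3. Size of the omission for OFF time**

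The documents give no rate of loss before a first valid diary, so a share e is assumed, equal in every arm. Restored tozadenant patients take the placebo mean, as the SAP's rule does for withdrawals, and restored placebo patients leave the placebo mean unchanged. If the mITT difference is 0.9 h:

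- difference in all randomized patients = 0.9 × (1 − e), with 150 per arm;
- comparator = the mITT itself, 0.9 h with 150 × (1 − e) per arm.

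Power is by noncentral t. It ignores later dropout in both analyses and the extra variance from imputation.

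| e (assumed) | Patients per arm | All-randomized difference | Power, all randomized | Power, mITT | Gap (points) |
|---|---|---|---|---|---|
| 2% | 3 | 0.882 h | 83.4% | 84.1% | 0.7 |
| 5% | 7.5 | 0.855 h | 81.0% | 82.9% | 1.9 |
| 10% | 15 | 0.810 h | 76.7% | 80.9% | 4.2 |

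At 2-5% the shift is 0.018-0.045 h, or 0.06-0.15 of the 0.30 h planning SE. The only related figure in the plan is that 80% are expected to complete Part A and continue (protocol 3.1.2). That covers all 24 weeks and does not say how many leave before a valid diary.

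**4. Who is left out of UPDRS II+III**

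Two groups can have a valid baseline and post-baseline UPDRS but no valid post-baseline diary:

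- (a) patients whose post-baseline diaries are all invalid;
- (b) patients who terminate before Week 2 and are assessed within 24 hours of the last dose.

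For group (b) the set definition is not the only barrier. SAP 9.6.1 treats week as a category (2, 6, 12, 18, 24). Protocol 11.8 carries Early Termination data to the next visit for OFF time only. Nothing assigns an Early Termination UPDRS to a week.

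The size of group (a) also depends on an unreconciled rule. SAP 4.1 and one paragraph of protocol 11.8 accept a single valid diary day for a visit; another paragraph of 11.8 requires two of three.

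**The case against.** The case against giving this weight is strong in several respects.

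- **The primary is untouched.** A patient with no post-baseline OFF time adds nothing to the MMRM, so the post-baseline diary condition costs it nothing. This stands.
- **The shift is small.** Against a 0.30 h standard error it is minor, and it appears in one sensitivity analysis. This stands.
- **An empty step is not an error.** SAP 9.6.2.2 says that some steps may not be needed. This stands as to the algorithm. It does not answer the point that the set removes the patients the step would serve.
- **The UPDRS groups are narrow.** Under the SAP one valid day suffices for a visit, patients are trained and reminded, diaries are centrally reviewed, and Early Termination UPDRS has the 24-hour limit. This stands, and it is why the fix needs a visit-mapping rule.
- **Protocol and SAP agree on the mITT.** This stands: the set is prespecified, and the point is an improvement to it, not a contradiction.

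A reader might infer that early intolerance differs between tozadenant and placebo, so that the sensitivity analysis is biased in the drug's favour. The documents do not support this, because they give no early-loss rate by arm. The fall below 0.9 h in the table follows from the placebo-mean rule and is not evidence of differential loss. A reader might also set the plan's 85% against 83-81% and see a loss of 2-4 points. That overstates it, because the mITT analysis would itself have fewer than 150 per arm.

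**Conclusion.** The point holds in limited form. Patients with no valid post-baseline diary are outside every efficacy treatment comparison, including the placebo-based imputation, and the diary condition can drop valid UPDRS II+III data from confirmatory test 3. It would be wrong to say that the imputation misses dropouts in general, or that Early Termination UPDRS is always available.

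For OFF time, with an assumed 2-5% of each arm affected equally and restored tozadenant patients taking the placebo mean, the difference moves from 0.9 h to about 0.88-0.86 h, and power is about 1-2 points below the mITT analysis. At an assumed 10% the figures are 0.81 h and about 4 points. The direction of any bias from differential loss is unknown. The documents do not allow a size for UPDRS, so no effect on the 60 mg tests can be claimed beyond the fact that they wait behind test 3. This is a cheap improvement worth making, not a threat to the primary result.

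**What to change.** 1. Keep the mITT MMRM as the primary analysis.
2. In SAP 9.6.2, add a placebo-based imputation run in all randomized patients with a valid baseline diary. The existing first monotone step then has patients to work on.
3. In SAP 9.6.3, analyse UPDRS II+III in all treated patients with a valid baseline and at least one valid post-baseline UPDRS, whatever their diary status. If the confirmatory set cannot be changed, for instance because of the Special Protocol Assessment, prespecify this as a supportive analysis.
4. State that an Early Termination UPDRS is assigned to the next scheduled visit, as protocol 11.8 does for OFF time. Without this rule, item 3 does not bring the pre-Week-2 terminators into the model.
5. Reconcile the one-day and two-of-three-day rules for a valid diary visit, since they decide who is in the mITT.

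The cost is SAP wording before unblinding and one more analysis run. The SAP was written against protocol Amendment 1 and the protocol is now at Amendment 3, so these changes can go into an update. The downside is that the sensitivity estimate may be slightly less favourable.
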